13.4.2 Interim analysis for primary endpoint (iDFS)

Early stopping for futility is defined under a one-sided hypothesis of clinical benefit of aspirin and will be conducted using standard group sequential designs for phase III studies of time-to-event outcomes. Specifically, the Z-statistics from stratified log-rank tests will be calculated at each interim analysis. Futility boundaries will be defined using a Hang, Shih and DeCanis Gamma beta-spending function (parameter = -5) whereby the futility boundary at the first interim analysis is close to observing no treatment effect with aspirin (HR = 1) [23]. Interim monitoring for futility will begin at the first DSMB meeting to occur when 50% of expected events are observed and continue to coincide with the semi-annual calendar of the board.

In addition to the boundary and observed Z-statistics, the DSMB will be provided Kaplan-Meier product limit estimators to the survival functions for each arm, and the corresponding hazard ratio (corr. HR) and 95% CIs from a stratified Cox proportional hazard model for iDFS.

The following table provides boundaries under the assumed rates of accrual and target hazard rates of iDFS that results three interim analyses for futility starting at exactly 50% information.

	First Interim	Second Interim	Third Interim	Final Analysis
iDFS Events:N (%)	191 (50%)	247 (65%)	305 (80%)	381 (100%)
Months from activation	34	40	46	54
Futility Bound critical Z (corr. HR)	-0.192 (1.03)	0.385 (0.96)	0.988 (0.89)	-
Superiority Bound: critical Z (corr.HR)	-	-		1.96 (0.82)
Nominal Alpha (Superiority)	-	-		0.025
Accumulated Alpha	-	-		0.025
Accumulated Beta	0.015	0.033	0.071	0.194

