13.2 Sample Size, Accrual Time and Study Duration

A stratified log-rank test will be used for the primary comparison of iDFS, with an overall one-sided Type I error of 0.025. Five year iDFS on placebo is assumed to be 77% based on results from the control arm of E5103. This study randomized 4994 patients to doxorubicin, cyclophosphamide, and paclitaxel plus or minus bevacizumab, and the patient population was similar to current eligibility criteria. An improvement in 5year iDFS to 82.2% would be considered clinically meaningful (HR = 0.75) and consistent with published data. Final analysis will occur at 381 iDFS events, in order to have 80% power to detect the target improvement.

A total sample size of 2936 patients will be enrolled in order to reach 381 iDFS events for final analysis. This assumes an accrual duration of 30 months including a 6 month ramp-up period to a maximum of 108 patients per month, and a constant hazard of loss-to-follow-up rate of 5% at 48 months in each arm.

An additional follow-up of 24 months is anticipated to reach final analysis, for a total study duration of 54 months from activation.

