Because accrual was slower than anticipated, the eligibility criteria have been expanded although the sample size and overall analytic plan remain unchanged. Originally, subjects must have histologically confirmed invasive breast cancer and register within 12 months of initial diagnosis. The eligibility criteria have been extended to within 18 months of initial diagnosis for hormone receptor negative patients (HR-), and patients with hormone-receptor positive disease (HR+) would be eligible to participate within 10 years from initial diagnosis if there is no evidence of local/regional recurrence or metastatic disease. With the proposed change in study population, the primary objective will remain to compare the invasive disease free survival (iDFS) of patients randomized to receive aspirin (300 mg daily) versus placebo, and is defined as the interval from the defined as time from randomization to the first occurrence of any one of the following events for invasive disease: Distant recurrence, locoregional recurrence, ipsilateral or contralateral breast cancer, second primary (non-breast) invasive cancer or death from any cause as per section 13.3, and the primary analysis will be performed in an intention-to-treat manner, in which all patients including those who do not begin protocol therapy will be analyzed according to their assigned arm (13.3.3). The target effect-size will remain a 25% improvement in outcomes with the intervention (HR = 0.75), and under the assumption the risk of recurrence in HR+ disease is approximately constant even up to 20 years out from diagnosis (66), the number of iDFS events for final analysis would be reached under comparable timelines with the target sample size of 2936 patients. With the modification, the HR status stratification factor has been modified to be HR-positive patients that are less than or greater than 18 months out from initial diagnosis, and HR-negative patients, and a secondary analysis will be done to compare the efficacy in the subgroup of patients within 18 months of diagnosis, and explore outcomes and relationship to treatment in patients more than 18 months out from initial diagnosis with disease-free interval included as a covariate in multivariate regression models.

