13.4 Study Monitoring and Interim Analysis

13.4.1 Study monitoring

Interim monitoring will be conducted by the Alliance Data and Safety Monitoring Board (DSMB) and will be scheduled to coincide with the semi-annual calendar of the board's meetings. Under standard monitoring procedures, the DSMB will consider evidence regarding safety (adverse events, adherence) and the feasibility of completing the trial (accrual rate).

Adherence will be reported to the DSMB using descriptive statistics to summarize by arm compliance to study treatment and non-protocol use of aspirin and NSAIDs. For compliance, the proportion that completed 80% of the total number of study tablets over the past period (6 months) and a 95% confidence interval will be reported for the number of patients on treatment at each study visit. P-values from a two-sided Fisher exact test will

be provided to the DSMB to help with interpretation of the data, but they are not considered as formal hypothesis tests and will not trigger any decision rule on study status.

In addition, formal interim analyses are to be conducted to consider early stopping for futility. These interim analyses are timed to occur after 50% of the total number of iDFS events are observed in order to be sensitive to the known heterogeneity of recurrence rates over time for the two subpopulations of triple negative versus HmR-positive breast cancer, in which the former disease tends to recur earlier than the latter disease. Therefore, there will be no early stopping for superiority of aspirin over placebo in order to be able to fully address the question of treatment effect by breast cancer subtype.

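### Second-interim futility bound is printed as Z 0.385, which contradicts its own hazard ratio (0.96), its accumulated beta (0.033) and the stated spending rule, which gives 0.358

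*Combined protocol and SAP*

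**What the plan says.** Section 13.2 sets the test "with an overall one-sided Type I error of 0.025" and the target effect: "An improvement in 5year iDFS to 82.2% would be considered clinically meaningful (HR = 0.75"). The final analysis is at 381 iDFS events with 80% power. Section 13.4.1 rules out early stopping for superiority, so the interim bounds are for futility only.

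Section 13.4.2 gives the rule: "Futility boundaries will be defined using a Hang, Shih and DeCanis Gamma beta-spending function (parameter = -5"). The table is introduced as a projection: "The following table provides boundaries under the assumed rates of accrual and target hazard rates of iDFS". Its entries are:

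| | Look 1 | Look 2 | Look 3 | Final |
|---|---|---|---|---|
| iDFS events (information) | 191 (50%) | 247 (65%) | 305 (80%) | 381 (100%) |
| Critical Z (HR) | -0.192 (1.03) | 0.385 (0.96) | 0.988 (0.89) | 1.96 (0.82) |
| Accumulated beta | 0.015 | 0.033 | 0.071 | 0.194 |

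On use, the section says: "In addition to the boundary and observed Z-statistics, the DSMB will be provided Kaplan-Meier product limit estimators".

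**The concern.** The Z, the hazard ratio and the accumulated beta in one column describe the same boundary, so each should follow from the others. In the second-interim column they do not: the Z disagrees with both figures printed beside it.

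The table holds the stopping thresholds for the primary endpoint, and the DSMB compares its observed statistic with the boundary. If 0.385 were used as a fixed threshold near 247 events, a stratified log-rank Z between 0.358 and 0.385 would count as crossing for futility when the plan's own rule says it does not. A member who worked from the printed hazard ratio would infer a different bound from one who worked from the printed Z.

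**Working it through.** **Inputs.** From 13.1: 1:1 allocation. From 13.2: HR 0.75, one-sided 0.025, 381 events, 80% power. From 13.4.2: gamma parameter -5 and the table above. The log-rank information at D events is taken as D/4, so Z has mean ln(1/0.75)·√D/2 under the target, and the correlation between looks i < j is √(Di/Dj).

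**Anchor.** The Schoenfeld formula gives 380 events for 80% power, and 381 events give power 0.802. The plan's own sizing therefore reproduces on this basis.

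**1. Z against hazard ratio.** HR = exp(-2Z/√D).

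| Look | D | Printed Z | HR from Z | Printed HR |
|---|---|---|---|---|
| 1 | 191 | -0.192 | 1.028 | 1.03 |
| 2 | 247 | 0.385 | 0.952 | 0.96 |
| 3 | 305 | 0.988 | 0.893 | 0.89 |
| Final | 381 | 1.96 | 0.818 | 0.82 |

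Only look 2 fails. Solving for a hazard ratio that prints as 0.96 (0.955 to 0.965) at 247 events gives Z from 0.280 to 0.362. About 280 events would be needed before Z 0.385 printed as 0.96. This check uses no spending function, drift or total beta.

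**2. Z against accumulated beta.** This is the probability, under HR 0.75, of having crossed by look 2, with the printed first bound of -0.192 at 191 events.

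- Z 0.385 at 247 events accumulates 0.0342, which prints as 0.034.
- A value that prints as 0.033 (0.0325 to 0.0335) needs Z from 0.355 to 0.372.

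Checks 1 and 2 together leave Z from 0.355 to 0.362. The lower end depends on the assumed drift; with drift z(0.975)+z(0.80) it is 0.349. The upper end comes from the hazard ratio and does not depend on drift.

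**3. Z against the stated rule.** Cumulative spending is β(t) = B·(exp(5t) - 1)/(exp(5) - 1). The section names no total, so B is taken as the table's final accumulated beta, 0.194. The bounds are then solved in sequence at t = 0.50, 0.65 and 0.80.

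| Look | β(t) | Z from rule | HR | Printed Z (HR), beta |
|---|---|---|---|---|
| 1 | 0.0147 | -0.192 | 1.028 | -0.192 (1.03), 0.015 |
| 2 | 0.0326 | 0.358 | 0.956 | 0.385 (0.96), 0.033 |
| 3 | 0.0705 | 0.988 | 0.893 | 0.988 (0.89), 0.071 |

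Every printed interim futility figure is recovered except 0.385. Totals from 0.1935 to 0.1945, all of which print as 0.194, move the second bound only between 0.357 and 0.359.

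**4. Consequence.** These use looks at 191, 247, 305 and 381 events with a final bound of 1.96.

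| | Look 2 at 0.385 | Look 2 at 0.358 |
|---|---|---|
| Accumulated beta by look 2 | 0.0342 | 0.0327 |
| Stopped by look 2 if HR = 1 | 66.2% | 65.3% |
| Overall type II error | 0.2034 | 0.2032 |
| Type I error if futility stops are followed | 0.0244 | 0.0244 |

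The excess is 0.385 - 0.358 = 0.027 in Z. In hazard ratio it is about 0.955 - 0.952 = 0.003. That conversion is approximate, because the hazard ratio the DSMB sees comes from a stratified Cox model.

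**The case against.** The strongest objection is that the replacement value depends on how the looks are represented. The value 0.358 comes from exactly 50/65/80% of 381, which is 190.5, 247.65 and 304.8 events. At the whole counts of 191, 247 and 305, the same rule gives -0.187, 0.350 and 0.991, with accumulated beta at look 2 of 0.0323, which prints as 0.032. This is true, but those values miss the printed first and third bounds, whereas the exact fractions match both to three decimals. The exact fractions are therefore very probably what was used, and 0.385 fails on either basis.

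Second, the total of 0.194 is inferred, and the table does not close on it. With the printed bounds and a final bound of 1.96, overall type II error computes to about 0.203. That stands as a separate discrepancy in the final column. Check 1 uses neither a total nor a drift, and check 2 uses no total.

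Third, another convention might produce 0.385. Alternatives were tried for the drift, event split, total beta, gamma (-4 to -6) and form of the hazard ratio, and none gave 0.385 while keeping the other two bounds. With drift z(0.975)+z(0.806), Z 0.385 does accumulate 0.0333 and so passes the beta check. It still fails the hazard-ratio check, and with a total of 0.20 the bounds become -0.169, 0.3845 and 1.018, so looks 1 and 3 no longer match.

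Fourth, the operating rule is the spending function, and the table is only a projection. Reviews are "scheduled to coincide with the semi-annual calendar", the timing sentence reads "Interim monitoring for futility will begin at the first DSMB meeting to occur when 50% of expected events are observed", and 13.2 reports "Because accrual was slower than anticipated, the eligibility criteria have been expanded". A look at exactly 247 events is therefore unlikely. The rule's second bound is 0.269 at 240 events and 0.443 at 255, or about (0.443 - 0.269)/15 = 0.012 per event, so a recomputed bound would not use the printed cell at all. This limits the practical effect and is why the point is minor. However, the section never says outright that bounds are recomputed at the observed count.

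A reading error in the table cannot be excluded, but nothing suggests one. Checking against the design output covers it.

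**Conclusion.** The printed second-interim Z of 0.385 is wrong as it stands. It contradicts the hazard ratio and the accumulated beta in its own column, and the rule the section states. The hazard-ratio contradiction needs only 1:1 allocation and the event count. The value 0.358 rests on exact information fractions, drift ln(1/0.75) with information D/4, and a total beta of 0.194. The digits look transposed, but the documents do not say so.

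Severity is minor. The printed bound makes futility stopping at the second look slightly easier, by 0.9 percentage points under no effect (66.2% - 65.3%). It costs essentially no power and does not inflate type I error.

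**What to change.** Check the second-interim cell against the original design output and change Z from 0.385 to 0.358, the value at exactly 65% information. Leave the hazard ratio of 0.96 and the accumulated beta of 0.033 as printed.

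Add one sentence to 13.4.2: the table is a projection, and the futility bound at each look is recomputed from the spending function at the observed number of iDFS events. State the total beta in the same place, so that the recomputation is defined.

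The cost is one cell and a line or two of text. Event counts, sample size, alpha, stated power and the other interim entries do not change.

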13.5 Statistical Section for Lifestyle Measures of Inflammation

Studies to evaluate epidemiologic measures of lifestyle that are potential pro-inflammatory states and modifying factors will be performed after the primary analysis to compare iDFS in patients randomized to receive aspirin versus placebo is completed. Studies to evaluate inflammatory markers from banked tumor and germline DNA, plasma and urine will be performed retrospectively once the primary analysis is completed and laboratory assays have been identified. The following statistical methods will be used in the analysis plans for secondary objectives relating to lifestyle measures and inflammatory markers derived from banked specimens.

Descriptive statistics (mean, standard deviation, median, interquartile range and range) will be used to summarize all quantitative measures obtained at baseline and at 2 years. Absolute change from baseline to the 2 year assessment will be summarized accordingly for patient reported instruments. For inflammatory markers, difference scores will be summarized and evaluated using either absolute or fold-change depending on background information for each assay output.

The following thresholds will be used to summarize lifestyle measures at baseline and at 2 years, and to define patient subgroups for evaluating differential treatment effects: Body mass index (BMI) categories will be defined according to the World Health Organization as underweight ($<18.5 \text{ kg/m}^2$) or normal weight ($18.5\text{-}24.9 \text{ kg/m}^2$) versus overweight ($25\text{-}29.9 \text{ kg/m}^2$) or obese ($\text{BMI} \geq 30 \text{ kg/m}^2$). The anticipated prevalence of overweight (30%) and obese (36.5%) patients are taken from Centers for Disease Control and Prevention report for US Women age 20 years or older [24]. Physical activity categories by a modified Paffenbarger questionnaire will be defined as sedentary ($< 3 \text{ METs}$, 32% prevalence) versus CDC recommended ($3\text{-}8.9 \text{ METs}$, 29% prevalence) or active ($\geq 9 \text{ METs}$, 39% prevalence) [25]. Sleep will be assessed with the Pittsburgh Sleep Quality Index (PSQI) with scores ranging from 0 to 21 and poor quality sleep defined as great than 5 [26]. The mean PSQI was 5.5 and 6.7 in cohorts of middle age white and black women, respectively [27]. A median PSQI of 9 was reported in early stage breast cancer patients with aromatase inhibitor induced musculoskeletal symptoms [28]. Depression will be assessed by the Center for Epidemiologic Studies-Depression scale-Revised (CESD-R) with scores ranging from 0 to 6 and possible depression defined as ≥ 16 [29, 30]. Median CESD-R as 10.5 in early stage breast cancer patients with aromatase inhibitor induced musculoskeletal symptoms [28]. The Perceived Stress Scale (PSS) will be assessed using the 10 item scale (PSS-10) with scores less than 16 defining "normal" for breast cancer patients [31] with a prevalence of 61% in early stage breast cancer patients 12 months after initiation of chemotherapy [32]. Secondary and exploratory analysis will evaluate the lifestyle measures listed above as continuous factors and will evaluate individual items from the Brief Pain Inventory (BPI) dichotomized at ≥ 4 on the 0-10 Likert scales [33]. Pain had a reported prevalence of 21% in early stage breast cancer patients taking aromatase inhibitors [34].

The hypothesis is that subgroups of participants, defined by lifestyle factors that are potential pro-inflammatory states, would receive greater treatment benefit from aspirin. The potential for any baseline state to modify the effect of treatment upon iDFS and OS will be evaluated using multivariate Cox proportional hazards models that include study stratification factors main effects and pairwise interaction between each dichotomous baseline factor and treatment arm. Simultaneous testing of the lifestyle factors will be performed, using a single likelihood ratio test (LRT) of a "full" model with all terms versus a "reduced" model with only main effects for treatment assignment, study stratification factors, and lifestyle factors. The LRT for the multivariable Cox regression model will use an alpha = 0.05. If the "full" model is found to be superior under the LRT, a stepwise backward-selection process will be used to identify the set of individual factors with the strongest interaction with treatment assignment, using a nominal

$p < 0.05$ for inclusion in the final model. The following table proves the effect sizes there will be 80% power to detect using the method of [35] for a marginal bivariable test with time-to-event data. Effect sizes are calculated for varying prevalences of pro-inflammatory states, assuming a quantitative interaction and final analysis occurs when 381 IDFS events (216 events in the placebo arm and 165 events in the aspirin arm).

Prevalence	Ratio of HRs
50%	0.56
40%	0.55
30%	0.53
20%	0.48

Association of measures of inflammatory states, factors or markers at 2-years with clinical outcome will be explored using landmark analyses of IDFS and OS in the subset of patients that are evaluable and event-free. All adjusted HRs and ratios of HRs from the final multivariable models will be reported with 95% confidence intervals. Hypothesis tests of inflammatory markers from banked biospecimen will be exploratory and hypothesis-generating using a nominal two-sided alpha = 0.05 for each analyte, and estimates of the false discovery rate (FDR) for multiple inflammatory markers that are potentially correlated will be obtained using the resampling-based Yekutieli-Benjamini method [36].

The pairwise correlations of baseline immune markers, states and factors, and changes from baseline, will be estimated within and across treatment arms using Spearman coefficients with empirical 95% confidence intervals drawn from the BCA bootstrap method. Unsupervised learning methods (e.g. agglomerative hierarchical clustering with Spearman correlation as the measure of distance) will be used to look for patterns of correlation among any multi-analyte markers of inflammation.

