2.2 Secondary Objectives

2.2.1 To compare the effect of aspirin versus placebo in early stage HER2 negative breast cancer patients upon:

- a) Distant disease-free survival
- b) Overall survival
- c) Cardiovascular disease (see [Section11.3](#))

2.2.2 To compare the toxicity of aspirin versus placebo in early stage HER2 negative breast cancer patients.

2.2.3 To assess adherence to aspirin and placebo among early stage HER2 negative breast cancer patients.

2.2.4 To bank tumor and germline deoxyribonucleic acid (DNA), plasma and urine collected at baseline and sequential plasma and urine collected 2 years later for future measurement of inflammatory markers.

2.2.5 To determine if there are subgroups of participants characterized by lifestyle factors associates with greater inflammation for whom there is greater benefit of aspirin versus placebo upon iDFS.

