15.0 BIOSPECIMEN COLLECTION

15.1. Rationale

Although we do not currently have funding to perform biomarker analyses but we do have funding for the collection and processing of specimens, so we have decided to pursue a pragmatic approach of collecting biospecimens now, which will be at two time points: baseline prior to starting the intervention and after two years on study. Two years was chosen as the second collection time since that would present a uniform time for all subjects and would be within the time frame of the Department of Defense funding. Tumor blocks will also be collected at baseline. The plan for testing the banked samples will include a specific background, methods, and statistical section and will be submitted to NCI to be reviewed and approved according to NCTN procedures before any testing is done. As detailed in section 6, all biospecimens will be stored at the Alliance Biorepository at Washington University of St. Louis.

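### Section 13.5 evaluates plasma and urine inflammatory markers by difference scores and names no baseline adjustment; naming it costs almost nothing and never loses precision in large samples

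*Combined protocol and SAP*

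**What the plan says.** Objective 2.2.4 is to bank specimens, including "sequential plasma and urine collected 2 years later for future measurement of inflammatory markers". Section 15.1 gives the two collection times as "baseline prior to starting the intervention and after two years on study". The table in Section 6.3 shows blood and urine at both times and tumor tissue before treatment only; participation is optional.

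Section 13.5 states its scope: "The following statistical methods will be used in the analysis plans for secondary objectives relating to lifestyle measures and inflammatory markers". For patient-reported instruments it asks only that absolute change be summarized. For inflammatory markers it goes further: "difference scores will be summarized and evaluated using either absolute or fold-change depending on background information for each assay output". Later in the section: "Hypothesis tests of inflammatory markers from banked biospecimen will be exploratory and hypothesis-generating using a nominal two-sided alpha = 0.05 for each analyte". That sentence does not say which contrast is tested. The last paragraph adds: "The pairwise correlations of baseline immune markers, states and factors, and changes from baseline, will be estimated within and across treatment arms using Spearman coefficients".

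Section 15.1 defers the detail: "The plan for testing the banked samples will include a specific background, methods, and statistical section and will be submitted to NCI", with approval required before any testing. No section names a model in which the 2-year marker value is adjusted for its baseline value.

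**The concern.** A difference score fixes the slope on baseline at 1. Unless that is the true slope, an unadjusted comparison of difference scores carries baseline noise that a covariate would remove. The baseline sample is already in the bank, so the lost precision buys nothing.

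The second issue is the correlation paragraph. A change from baseline contains the baseline value with a minus sign. If a marker's change is correlated with its own baseline, a negative coefficient can appear when nothing has happened biologically. Within the aspirin arm, or pooled over arms, a reader could take this to mean that patients with more inflammation respond more. That resembles the hypothesis in Sections 13.5 and 14.1.1 that aspirin helps such patients most.

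**Working it through.** **Stated figures.** The documents give no sample size, standard deviation, effect or power for any marker analysis, so there is no marker figure to reproduce. The interaction table in Section 13.5 does reproduce. With 216 and 165 events, 50% prevalence and two-sided 0.05, the ratio is exp(-(1.960 + 0.842) × sqrt(2/108 + 2/82.5)) = 0.56, as stated. It does not enter this point.

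**Inputs.** Two measurements per marker and 1:1 allocation come from Sections 6.3 and 7.0. The baseline to 2-year correlation r and the ratio k of the 2-year to the baseline standard deviation are assumptions, shown over a range. Section 15.2 offers only a qualitative remark that some urinary measures are stable over time.

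**Step 1: variance of a between-arm comparison.** In units of the baseline variance, the residual variance is 1 + k² - 2rk for the unadjusted difference and k²(1 - r²) for ANCOVA. Their ratio is

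(1 + k² - 2rk) / (k²(1 - r²)) = 1 + (1 - rk)² / (k²(1 - r²)).

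The second term cannot be negative, so in large samples adjustment never costs precision. With k = 1 the ratio is 2/(1 + r).

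**Step 2: what that means for power.** Where the unadjusted difference has 80% power at two-sided 0.05, ANCOVA has Φ(2.8016 × sqrt(2/(1 + r)) - 1.96).

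**Step 3: a marker against its own change.** The correlation is (rk - 1)/sqrt(1 + k² - 2rk). It is negative whenever rk < 1. With k = 1 it is -sqrt((1 - r)/2).

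Results with equal standard deviations (k = 1):

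| r | Variance ratio | Excess | ANCOVA power where difference has 80% | Correlation with own change |
|---|---|---|---|---|
| 0.3 | 1.54 | 54% | 93% | -0.59 |
| 0.5 | 1.33 | 33% | 90% | -0.50 |
| 0.7 | 1.18 | 18% | 86% | -0.39 |
| 0.9 | 1.05 | 5% | 82% | -0.22 |

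At r = 0 the excess is 100%.

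**Step 4: unequal standard deviations.**

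- k = 0.8, r = 0.5: 1 + 0.36/0.48 = 1.75, a 75% excess.
- k = 1.5, r = 0.5: 1 + 0.0625/1.6875 = 1.04, a 4% excess.
- k = 1.25, r = 0.8: rk = 1, so there is no excess and the own-change correlation is 0.
- k = 1.5, r = 0.8: the own-change correlation is +0.22.

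**Step 5: simulation check.** With 400 patients, equal standard deviations and no treatment effect, the simulated variance ratios were 1.52, 1.37 and 1.19 at r = 0.3, 0.5 and 0.7. Spearman correlations of baseline with own change were -0.57, -0.48 and -0.37, so ranking does not remove the coupling.

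**The case against.** The case for leaving the text alone has several parts.

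- **No contrast is named.** Objective 2.2.4 is banking only, and the marker tests are exploratory. A reader might infer that the plan commits to estimating aspirin's effect on markers from raw changes, or that this is the trial's only check of mechanism. The documents say neither. This stands, and it makes the precision point conditional.
- **A difference score is a metric, not a model.** Regressing the difference on arm with baseline as covariate gives the same arm estimate and standard error as ANCOVA of the 2-year value. So 13.5 does not forbid adjustment. That is correct, but it does not ask for adjustment either.
- **The detail is deferred to a later approved plan.** It is, but 13.5 says its methods will be used there, so an unadjusted difference is what that plan inherits by default.
- **The size is unknown.** A reader might put the excess at up to about 50%. That figure needs r of about 1/3 with equal standard deviations, which the documents do not give, and it is not a maximum. The remark in 15.2 on stable urinary measures points toward higher r and a smaller excess.
- **Not every correlation is affected.** A reader might infer that all baseline-by-change correlations are negative by construction. The result covers a marker paired with its own change, and only when rk < 1. The paragraph may intend correlations among baselines and, separately, among changes; it does not say so, and it does not exclude own-change pairs.
- **Regression to the mean cancels in expectation between randomized arms.** It does. The lifestyle hypothesis is tested by Cox interaction terms for iDFS and OS, which use no change scores. The risk of misreading is therefore confined to within-arm or pooled correlations.

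**Conclusion.** The point holds as a low-consequence improvement. Section 13.5 makes the difference score the only stated metric for evaluating plasma and urine markers, plans a test per analyte and names no baseline adjustment. If arms are compared on unadjusted differences, the variance is 5% to 54% higher than with adjustment for r from 0.9 to 0.3 with equal standard deviations. The excess is larger at lower r. It changes with the standard deviation ratio but is never negative in large samples. Own-baseline-by-own-change correlations are negative without any biological effect whenever r times the standard deviation ratio is below 1.

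Both r and the standard deviation ratio are assumptions, and so is the existence of an unadjusted arm comparison. Tumor markers fall outside the point because tissue is collected once. The marker work is exploratory and, by Section 15.1, not yet funded. Nothing here affects iDFS, alpha, the sample size or the interaction test.

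**What to change.** In Section 13.5:

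1. State that any between-arm comparison of a 2-year plasma or urine marker uses ANCOVA, with the marker's baseline value and the stratification factors as covariates. Both marker values are on the log scale where fold-change is intended.
2. Keep absolute and fold-change difference scores as descriptive summaries.
3. In the correlation paragraph, exclude pairs of a marker's baseline with its own change, or replace raw change by baseline-adjusted change (the residual from regression on baseline).

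The marker plan promised in Section 15.1 should carry the same wording, and since it must be approved before testing, the choice can still be prespecified. The cost is a few sentences of text and one line in the results explaining that the estimates are baseline-adjusted differences. No extra sample, visit, assay or patient is needed.
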